Vital signs	X	X	X	X	X	X	X	X	2-weekly	X	Including weight and height (height at Screening only)
ECOG PS ^d	X	X ^d	X	X	X	X	X	X	2-weekly	X	d: ECOG PS 0 or 1 is required at W1D1
12-lead ECG	X										
Laboratory Assessments											
Hematology and hemostaseology	X	X		X		X		X	4-weekly	X	Details on blood tests under this category is listed in Table 16 . Samples must also be drawn and results for core chemistry, hematology, and pregnancy test reviewed prior to dose administration. For participants who met study criteria at screening, but W1D1 values are not within study criteria and study continuation is desired, discuss with the Medical Monitor.
Core serum chemistry		X		X		X		X	4-weekly		Core serum chemistry are listed in Table 16 . Samples must also be drawn and results for core chemistry, hematology, and pregnancy test reviewed prior to dose administration. For participants who met study criteria at screening, but W1D1 values are not within study criteria and study continuation is desired, discuss with the Medical Monitor.
Full serum chemistry Panel A	X		X		X		X		4-weekly	X	See Table 16 for individual tests in each laboratory panel. Blood samples must also be drawn and results for core chemistry parameters, hematology, and pregnancy test reviewed prior to dose administration.
Full serum chemistry Panel B	X										See Table 16 for individual tests in each laboratory panel.
Urinalysis	X	As clinically indicated									

M7824 Assessment	Screening/ Baseline Assessments	Treatment Phase (±3 days)								End-of-Treatment Visit	Notes
	Day -28 to Randomization	V1	V2	V3	V4	V5	V6	V7	Until PD	On the Day of or Within 7 Days of Decision	
		W1	W3	W5	W7	W9	W11	W13			
β-hCG pregnancy test (only applicable to WOCBP)	X ^e	X		X		X		X	4-weekly		β-hCG should be determined from serum at Screening and from a urine or serum sample thereafter. Results of the most recent pregnancy test should be available prior to dosing of study intervention. e: If a confirmation of a participant's postmenopausal status is necessary, follicle-stimulating hormone and estradiol tests will be performed at Screening.
Free T4 and TSH	X				X			X	6 weekly		

CCI

M7824 Assessment	Screening/ Baseline Assessme nts	Treatment Phase (±3 days)							Until PD	End-of-Treatment Visit	Notes
	Day -28 to Randomiza tion	V1	V2	V3	V4	V5	V6	V7		On the Day of or Within 7 Days of Decision	
		W1	W3	W5	W7	W9	W11	W13			
	D1	D15	D29	D43	D57	D71	D85				

CCI

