AE = adverse event; β-hCG = beta-human chorionic gonadotropin; CR = complete response; CRT = chemoradiotherapy; CT = computed tomography; D = Day; ECG = electrocardiogram; ECOG PS = Eastern Cooperative Oncology Group Performance Status; EoT = End-of-Treatment; HBV = hepatitis B virus; HCV = hepatitis C virus; ICF = Informed consent form; iv = intravenous; MRI = magnetic resonance imaging; PD = progressive disease; PD-L1 = programmed death-ligand 1; PE = physical examination; PR = partial response; RT = radiation therapy; T₄ = free thyroxine; **CCI** TSH = thyroid-stimulating hormone; V = Visit; W = Week; WOCBP = woman of childbearing potential.

Table 2 Schedule of Assessments – Pembrolizumab Arm

Pembrolizumab Assessment	Screening/ Baseline Assessments	Treatment Phase (±3 days)								End-of-Treatment Visit	Notes
	Day -28 to Randomization	V1	V2	V3	V4	V5	V6	V7	Until PD	On the Day of or Within 7 Days of Decision	
		W1	W4	W7	W10	W13	W16	W19			
		D1	D22	D43	D64	D85	D106	D127			
Administrative Procedures											
Written informed consent	X										To determine the main study eligibility criteria ahead of full screening procedures, an ICF will be used.
Inclusion/exclusion/ Enrollment (if eligible)	X	X ^a									Enrollment will be after the confirmation of fulfilling all inclusion criteria and without matching any exclusion criterion. a: Confirmation of eligibility via an abbreviated checklist is required prior to dosing on W1D1.
Demographic data	X										
Medical history	X										
Documentation concomitant therapy	X	X	X	X	X	X	X	X	3-weekly	X	
Prior anticancer drug/radiotherapy/ procedures	X										
Virology serology (HBV and HCV)	X			X ^b		X ^b		X ^b	6 weekly ^b		b: Only applicable to participants with a history of HBV or HCV infection.

Pembrolizumab Assessment	Screening/ Baseline Assessments	Treatment Phase (±3 days)								End-of-Treatment Visit	Notes	
	Day -28 to Randomization	V1	V2	V3	V4	V5	V6	V7	Until PD	On the Day of or Within 7 Days of Decision		
		W1	W4	W7	W10	W13	W16	W19				
ECOG PS ^d	X	X ^d	X	X	X	X	X	X	X	3-weekly	X	d: ECOG PS 0 or 1 is required at W1D1
12-lead ECG	X											
Laboratory Assessments												

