* Efficacy analysis will be provided in addition to outputs for regular IDMC safety meetings only for efficacy assessments IDMC meetings.

Data handling after cutoff date:

Data after the cutoff will not be displayed in any listings or used for summary statistics, e.g. laboratory values of samples taken after data cutoff, AEs with onset date after data cutoff, etc. will not be included in any analysis or listing.

Stop dates are not affected by this rule, e.g. a stop date of AEs, which starts prior to the cutoff, but stopped after date of cutoff, will not be changed.

Data cut will occur before the analysis database creation process, i.e. on the SDTM in input to the process for the ADAM creation.

Pooling of centers:

Because of the high number of participating centers and the anticipated small number of participants randomized in each center data will be pooled across centers, and the factor center will not be considered in statistical models or for subgroup analyses.

Unscheduled assessments

As per database definition, the unscheduled safety assessments are always linked to a scheduled time point (each unscheduled assessment is linked to the previous scheduled time point). Safety data retrieved from an unscheduled time point (vital signs, ECG and laboratory data) will be analyzed according to the following scenario:

- For shift tables, they will be taken into account in the definition of the worst assessment during the study
- For description at each time post-baseline point, the first available result (in chronological order) will be taken into account in the analysis in case of multiple values.

For description at baseline, the last available result before randomization will be taken into account in the analysis in case of multiple values.

Presentation of continuous and qualitative variables:

Continuous variables will be summarized using descriptive statistics, i.e.

- number of participants (N), number of participants with missing values
- mean, standard deviation (StD)
- median, 25th Percentile - 75th Percentile (Q1-Q3),
- minimum and maximum.

If there are no missing values this should be indicated by a 0.

Qualitative variables will be summarized by counts and percentages.

Unless otherwise stated the calculation of proportions will be based on the number of participants of the analysis set of interest. Therefore, counts of missing observations will be included in the denominator and presented as a separate category.

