15.3 Clinical Laboratory Evaluation

Treatment emergent laboratory assessments are any sample collected during on-treatment period.

Laboratory values (including corresponding normal ranges) converted in standard units will be used for summary statistics and shift tables.

Laboratory results will be classified according to the NCI-CTCAE Version 5.0. Additional laboratory results that are not part of NCI-CTCAE will be presented according to the categories: low, normal and high (according to the laboratory normal ranges). Quantitative data will be examined for trends using descriptive statistics (mean, StD, median, Q1, Q3, minimum, and maximum) of actual baseline values, on-treatment values and changes from baseline to each on-treatment visit over time. The changes computed will be the differences from baseline. Participants without post baseline laboratory samples will be excluded from analyses with respect to values after the baseline. Qualitative data based on reference ranges will be described according to the categories (i.e. low, normal, and high).

Laboratory parameters with NCI-CTC grades available

Laboratory parameters with NCI-CTC grades available will be analyzed with their respective NCI-CTC name and direction of abnormality. For parameters which are graded with both low and high values, the toxicities will be summarized separately. Low direction toxicity grades at baseline and post-baseline will be set to 0 when the variables are derived for summarizing high direction toxicity, and vice versa.

For gradable parameters, the following summaries will be displayed by treatment arm:

- Number and percentage of participants by worst on-treatment grade (≥ 1 , ≥ 3 , ≥ 4)
- Shift in toxicity grading from baseline to highest on-treatment toxicity grade

The following figures will also be provided by treatment arm:

- Boxplots of the laboratory values by timepoint
- Boxplots of the change from baseline by timepoint

The definitions of toxicity grading for each parameter are available in the NCI-CTCAE toxicity grading version 5.0 (in Appendix 18.1 of this IAP).

For **WBC differential counts** (neutrophil, lymphocyte counts), the absolute value will be used when reported. When only percentages are available (this is mainly important for neutrophils and lymphocytes, because the CTCAE grading is based on the absolute counts), the absolute value is derived as follows:

Derived differential absolute count = (WBC count) * (Differential %value / 100)

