15.5 Other Safety or Tolerability Evaluations

ECG

A listing of ECG values will be provided with the following information: treatment arm, participant identifier, age, sex, race, ECG parameter and unit, ECG date and value. The listing will be sorted by treatment arm, participant identifier, ECG parameter, and ECG date. It will include ECG values collected at screening and at safety follow-up visits.

ECOG Performance Status

The ECOG shift from baseline to the highest score during the on-treatment period will be summarized by treatment arm. ECOG performance status will also be presented in a listing at each time point.

Safety analyses by PD-L1 statuses

Further analyses on TEAEs and AESI by PD-L1 assays statuses may be provided on IDMC request.

The following safety tables may be provided by PD-L1 High/Not High statuses for PD-L1 assays of interest (e.g. SP263 assay):

- TEAEs by Worst Grade, SOC and PT
- Overview of Infusion-Related Reactions
- Overview of Immune-Related AE
- Overview of TGF- β inhibition mediated skin TEAE
- Overview of Treatment-Related Anemia

Subset of participants with Haemoptysis, Gastrointestinal Haemorrhages or TEAE leading to Death

Specific listings may be provided for AEs of participants meeting at least one of the following criteria:

- haemoptysis : PT code = Haemoptysis
- Gastrointestinal haemorrhage: SMQ=20000108
- TEAE leading to death within 30 days from first IMP intervention

The following listings are considered:

Medical history listing showing the following information: participant identifier, treatment arm, haemoptysis (Y/N), gastrointestinal haemorrhage(Y/N), TEAE leading to death (Y/N), date of first infusion of trial drug, date of last infusion of trial drug, country, age, sex, race, reported medical history, start date of medical history, end date of medical history, relationship to study condition, ongoing, grade, medical history of bleeding events.

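### Worst-value chemistry and ECOG tables compare arms measured every 2 weeks and every 3 weeks: a modest tilt against M7824 when time on treatment is similar

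*SAP*

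**What the plan says.** **Analysis.** For graded laboratory parameters, SAP 15.3 tabulates by arm the "Number and percentage of participants by worst on-treatment grade" and the shift from baseline to the highest grade. Cumulative liver categories and plots of peak ALT or AST against peak bilirubin follow. SAP 15.5 states: "The ECOG shift from baseline to the highest score during the on-treatment period will be summarized by treatment arm". SAP Section 9 adds unscheduled values: "For shift tables, they will be taken into account in the definition of the worst assessment during the study". SAP 6.6 keeps laboratory evaluations and ECOG in the single analysis planned after the trial was discontinued. No visible text restricts these tables to common time points or reports how many assessments each participant had. The exposure-adjusted rates in SAP 15.2.5 cover adverse events only.

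**Measurement (Protocol 1.3).** The ECOG row reads "ECOG PS ^d X X ^d X X X X X X 2-weekly" for M7824 and "ECOG PS ^d X X ^d X X X X X X X 3-weekly" for pembrolizumab. M7824 core chemistry ("Core serum chemistry X X X X 4-weekly") falls at V1, V3, V5 and V7. Panel A falls at V2, V4 and V6, then 4-weekly, so the two alternate. On pembrolizumab the visits are 3 weeks apart, and each panel becomes 6-weekly after V7. Table 16 puts the liver, electrolyte and renal tests and glucose in both panels.

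**By-visit displays.** SAP 15.3 also summarizes "changes from baseline to each on-treatment visit over time". V7 is week 13 on M7824 and week 19 on pembrolizumab.

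**The concern.** The worst of 12 readings tends to be worse than the worst of 8 from the same person. If the arms are read side by side on a maximum while the protocol measures one arm more often, part of any difference comes from the visit calendar. Safety relative to pembrolizumab is a secondary objective, and immune-related hepatitis and nephritis are listed risks of M7824. Chemistry tables are therefore where a schedule artefact could be read as a signal.

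**Working it through.** The plan states no figure for this effect, so there is nothing to reproduce. The check rebuilds the schedules and applies the same risk to both arms.

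**1. Scheduled post-baseline assessments (Protocol Tables 1 and 2), M7824 versus pembrolizumab**

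| | to D85 | to D169 (week 25) | to D314 |
|---|---|---|---|
| ECOG | 6 v 4 | 12 v 8 | 22 v 14 |
| Chemistry, panels alternating | 6 v 4 | 12 v 8 | 22 v 14 |
| Chemistry, third Panel A mark at V7 | 6 v 4 | 12 v 6 | 22 v 9 |
| Hematology | 3 v 4 | 6 v 6 | 11 v 9 |
| Thyroid | 2 v 2 | 4 v 4 | 7 v 7 |

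The third row follows the text copy of Table 2. Column positions there are uncertain: the pembrolizumab ECOG row carries one mark more than there are visits.

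**2. Independent readings.** P(at least one abnormal) = 1 − (1 − p)^k, with the same p in both arms. The documents give no p, so 0.5% to 5% is an assumption. For k = 12 versus 8:
- p = 0.5%: 5.8% v 3.9%
- p = 1%: 11.4% v 7.7% (ratio 1.5)
- p = 2%: 21.5% v 14.9%
- p = 5%: 46.0% v 33.7%

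For hematology to D85 (3 v 4) at p = 1%: 3.0% v 3.9%, the opposite direction.

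**3. Persistence.** A simulated autocorrelated process with 1% point prevalence, to D169 with 12 v 8 readings, gives ratios of 1.5, 1.4, 1.2 and 1.1 for half-lives of 3.5, 14, 42 and 180 days. An episode of L days is seen with probability min(1, L/interval): 7/14 = 0.50 v 7/21 = 0.33 for 7 days, and 1 v 1 from 21 days on.

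**4. A correlated ALT model (assumed).** ALT/ULN is log-normal with median 0.55, and log-scale SD 0.45 between and 0.30 within persons.

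| | Scheduled visits only (12 v 8) | Plus End-of-Treatment and 28-day samples (14 v 10) |
|---|---|---|
| Maximum above ULN | 40.9% v 36.1% | 42.7% v 38.8% |
| Difference | 4.8 points | 3.9 points |

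Above 3×ULN, 12 v 8 readings give 0.64% v 0.48%, a difference of 0.16 points. This model contains no hepatitis events.

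**5. Sampling error.** SE = √[(0.41×0.59 + 0.36×0.64)/n] = 5.6 points at n = 150 per arm (300/2) and 4.0 at n = 292 (584/2).

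**6. Time on treatment.** Eight ECOG assessments take 8×2 = 16 weeks on M7824 and 8×3 = 24 weeks on pembrolizumab. M7824 treatment shorter in that proportion would equalize the counts.

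**7. After the change.** D43, D85, D127, D169 and every 6 weeks onward are scheduled chemistry and ECOG days in both arms. Counts become 2, 4 and 7 by D85, D169 and D314 in each arm. At p = 1% that gives 2.0%, 3.9% and 6.8% in both, a ratio of 1.0.

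**The case against.** The case for leaving the plan alone has several parts, and much of it limits the point.

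- **Direction is conditional.** The on-treatment period ends 30 days after the last dose or the day before subsequent therapy (SAP Section 9), so discontinuation patterns change the counts. This stands. A reader might infer that M7824 must look worse on laboratory tables generally; the documents do not support that, given step 6, the matching thyroid schedule and the early hematology schedule.
- **Size.** The independent-reading figures ignore within-person correlation. Under the correlated model the ALT difference falls to 4 to 5 points. That is below the SE at 150 per arm and about equal to it at 292, and the documents do not say the expansion took place. A claim that the calendar outweighs sampling error is not supported.
- **Sparser sampling.** The 12 versus 6 count may be a column shift in the text copy. Protocol Appendix 5 also mentions creatinine before every dose and liver tests before each infusion, and the Table 16 footnote on pre-dose review could be read as adding hematology. These passages need reconciling with the schedule tables. Until then, neither 12 versus 6 nor a shortfall in early anemia detection on M7824 is established. Anemia is in any case a Tier 1 adverse-event term in SAP 15.2.5.
- **Triggered monitoring.** Appendix 5 intensifies liver testing after a first abnormality in both arms, and unscheduled values feed the shift tables. Peak grade then depends largely on shared monitoring. This is fair, and another reason to expect little effect at high grades.
- **Descriptive status.** No test or interval is planned for these tables; formal between-arm contrasts are for adverse events. This stands.
- **By-visit alignment.** Nothing visible shows that visit 7 in one arm is set against visit 7 in the other, and output details are in a separate appendix. The gap is the absence of a stated rule.

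What remains is that the schedules differ, the statistic is an unadjusted maximum, and no visible rule corrects for it.

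**Conclusion.** The point holds for ECOG and for the chemistry analytes shared by core chemistry and Panel A. With similar time on treatment and no true difference, worst-value tables tilt low-grade or transient abnormalities against M7824. The size rests on assumed per-assessment probabilities and an assumed ALT distribution, and only the assessment counts come from the protocol. It does not extend to thyroid tests, and for scheduled hematology the tilt is reversed to week 13, subject to the pre-dose footnote. It is a reporting bias in descriptive displays with no bearing on the PFS or OS tests. It is worth correcting because the tables are still planned and the correction is cheap.

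**What to change.** - Keep the all-data worst-value tables, and print the number of assessments and the time on treatment per participant beside them.
- Add between-arm versions of the worst-grade, shift, liver-category and ECOG tables that use one scheduled value per participant per common 6-week calendar window (targets W7, W13, W19, W25 and so on). Take the nearest value and stop at a common follow-up time. State a tie rule: M7824 hematology at W5 and W9 is equidistant from W7.
- State that by-visit summaries and boxplots align the arms by study week, not visit number.
- Reconcile the pre-dose laboratory footnote and the Appendix 5 monitoring text with Tables 1 and 2.

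The cost is extra programming. The matched tables use fewer values and may miss short-lived abnormalities, which the all-data tables still show.

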15.4 Vital Signs

Vital signs data during on-treatment period will be summarized by treatment arm for the Safety analysis set.

All vital sign parameters will be summarized using descriptive statistics (mean, StD, median, Q1, Q3, minimum, maximum) of actual baseline values, on-treatment values and changes from baseline to each visit over time.

In addition, the maximum changes of vital sign measurements baseline to maximum changes after start of 1st treatment will be grouped as follows:

Table 9 Categories of Maximum Change from Baseline in Vital Signs

Body temperature increase from baseline < 37 °C, 37-<38°C, 38-<39°C, 39-<40°C, ≥40°C	< 1°C , 1-<2°C , 2-<3°C, ≥ 3 °C
Body weight increase	< 10%, ≥ 10%
Body weight decrease	< 10%, ≥ 10%
Heart rate increase from baseline <100 bpm ; ≥ 100 bpm	≤20 bpm, >20 – 40 bpm, >40 bpm
Heart rate decrease from baseline ≤50 bpm ; > 50 bpm	≤20 bpm, >20 – 40 bpm, >40 bpm
SBP increase from baseline <140 mmHg; ≥ 140 mmHg	≤20 mmHg, >20 – 40 mmHg, >40 mmHg
SBP decrease from baseline ≤95 mmHg; > 95 mmHg,	≤20 mmHg, >20 – 40 mmHg, >40 mmHg
DBP increase from baseline <90 mmHg; ≥ 90 mmHg	≤20 mmHg, >20 – 40 mmHg, >40 mmHg
DBP decrease from baseline ≤45 mmHg; > 45 mmHg,	≤20 mmHg, >20 – 40 mmHg, >40 mmHg

The following summaries will be prepared for vital sign parameters as grouped above considering only participants with post baseline values:

- Maximal shifts (changes in categories)

The following potentially clinically significant abnormalities in vital signs will be also summarized:

- ≤ 95 mmHg and decrease from baseline ≥ 20 mmHg in systolic blood pressure
- ≥ 140 mmHg and increase from baseline ≥ 20 mmHg in systolic blood pressure
- ≤ 45 mmHg and decrease from baseline ≥ 20 mmHg in diastolic blood pressure
- ≥ 90 mmHg and increase from baseline ≥ 20 mmHg in diastolic blood pressure
- ≤ 50 bpm and decrease from baseline ≥ 20 bpm in heart rate
- ≥ 100 bpm and increase from baseline ≥ 20 bpm in heart rate
- ≥ 10% weight increase
- ≥ 10% weight decrease

All vital signs will also be listed, baseline values and post-baseline values collected after the on-treatment period will be flagged in the listing. The listing will include treatment arm, participant identifier, age, sex, race, vital sign parameter, visit, date, on-treatment flag, value, unit, baseline value, and change from baseline. Listings will be sorted by treatment arm, participant identifier, vital sign parameter and vital sign measurement date.

15.5 Other Safety or Tolerability Evaluations

ECG

A listing of ECG values will be provided with the following information: treatment arm, participant identifier, age, sex, race, ECG parameter and unit, ECG date and value. The listing will be sorted by treatment arm, participant identifier, ECG parameter, and ECG date. It will include ECG values collected at screening and at safety follow-up visits.

ECOG Performance Status

The ECOG shift from baseline to the highest score during the on-treatment period will be summarized by treatment arm. ECOG performance status will also be presented in a listing at each time point.

Safety analyses by PD-L1 statuses

Further analyses on TEAEs and AESI by PD-L1 assays statuses may be provided on IDMC request.

The following safety tables may be provided by PD-L1 High/Not High statuses for PD-L1 assays of interest (e.g. SP263 assay):

- TEAEs by Worst Grade, SOC and PT
- Overview of Infusion-Related Reactions
- Overview of Immune-Related AE
- Overview of TGF- β inhibition mediated skin TEAE
- Overview of Treatment-Related Anemia

Subset of participants with Haemoptysis, Gastrointestinal Haemorrhages or TEAE leading to Death

Specific listings may be provided for AEs of participants meeting at least one of the following criteria:

- haemoptysis : PT code = Haemoptysis
- Gastrointestinal haemorrhage: SMQ=20000108
- TEAE leading to death within 30 days from first IMP intervention

The following listings are considered:

Medical history listing showing the following information: participant identifier, treatment arm, haemoptysis (Y/N), gastrointestinal haemorrhage(Y/N), TEAE leading to death (Y/N), date of first infusion of trial drug, date of last infusion of trial drug, country, age, sex, race, reported medical history, start date of medical history, end date of medical history, relationship to study condition, ongoing, grade, medical history of bleeding events.

Concomitant medications listing including: participant identifier, treatment arm, haemoptysis (Y/N), gastrointestinal haemorrhage(Y/N), TEAE leading to death (Y/N), date of first infusion of trial drug, date of last infusion of trial drug, country, age, sex, race, preferred term of concomitant medication, medication name, start date of concomitant medication, end date of concomitant medication, dose (units), frequency, route, reason for medication (indication), reason for medication, use of antithrombotic agents (Y/N), concomitant medication (taken any time during on-treatment).

Adverse Events listing including: participant identifier, treatment arm, haemoptysis (Y/N), gastrointestinal haemorrhage(Y/N), TEAE leading to death (Y/N), Date of first infusion of trial drug, Date of last infusion of trial drug, preferred term, investigator term, start or change date of AE, end date of AE, treatment-emergent AE (Y/N), duration of AE (days), day since first infusion of trial drug (days), day since most recent infusion prior to AE onset (days), relationship to trial drug, grade, causality factor, action taken on trial drug, outcome, seriousness, country, age, sex, race, date of initial cancer diagnosis, TNM classification at initial diagnosis, TNM classification at study entry, prior anticancer therapy, tumor histology, tumor location, bleeding events in medical history (Y/N), PT of bleeding events in medical history, antithrombotic agents (any prior or concomitant medication of ATC code B01), last available collection date of hematology test, hemoglobin value (g/L), Platelets value ($10^9/L$), last available collection date of coagulation tests, PT value (sec), aPTT value (sec), INR value (ratio).

Subset of participants with ALP increase TEAE or Elevated ALP of Grade ≥ 1 during On-Treatment

On IDMC request, a specific listing may be provided for participants meeting at least one of the following criteria:

- increased ALP TEAE
- elevated ALP of grade ≥ 1 on treatment

This listing will include, subject with increased ALP TEAE (Y/N) , Subject with elevated ALP of grade ≥ 1 on treatment (Y/N), Analysis Visit, Analysis Date, Analysis Relative Day, On-Treatment Flag, ALP value, ALP ULN, Ratio ALP value/ULN, ALP toxicity grade, ALT value, ALT ULN, Ratio ALT value/ULN, ALT toxicity grade, AST value, AST ULN, Ratio AST value/ULN, AST toxicity grade, Bilirubin value, Bilirubin ULN, Ratio Bilirubin value/ULN, Bilirubin toxicity grade, GGT value, GGT ULN, ratio GGT value/ULN, GGT toxicity grade.

16 Analyses of Other Endpoints

CCI

CCI

CCI

CCI

CCI

CCI

CCI

CCI

CCI

